#### **11.6.1.2 Dermatology Life Quality Index**

The DLQI is a validated questionnaire with content specific to those with dermatology conditions. It consists of 10 items addressing the subject's perception of the impact of their skin disease on different aspects of their quality of life over the last week such as dermatology-related symptoms and feelings, daily activities, leisure, work or school, personal relationships, and the treatment (29). Each item is scored on a 4-point Likert scale (0 = 'not at all/not relevant'; 1 = 'a little'; 2 = 'a lot'; 3 = 'very much'). The total score is the sum of the 10 items (0 to 30); a high score is indicative of a poor quality of life. The DLQI will be completed at the trial site according to the schedule of trial procedures (Section 4).

### **11.6.1.3 Exit interviews (optional, selected countries only)**

Qualitative, semi-structured exit interviews will be conducted with a subgroup of 20-30 subjects by experienced qualitative interviewers after the end of the treatment period (i.e. after Week 6 or early termination). The exit interviews will only be conducted in selected countries to reduce the number of languages.

The exit interviews will be conducted by telephone, in the subject's native language, at a date and time agreed with the subject at the Week 6 visit. The interviews will be scheduled to occur as soon as possible after Week 6 and within a maximum of 2 weeks. The participants will be the first 20-30 subjects who agree to take part in the exit interviews. Up to 8 of the interview participants can be subjects who withdraw from the trial prior to Week 6. These subjects will be interviewed within 2 weeks after their withdrawal from the trial.

Efforts will be made to ensure that the subgroup is representative of the general patient population with regards to age, sex, and baseline DLE severity.

Each interview is expected to last approximately 60 minutes. A semi-structured interview guide will be used to explore the lived experience of DLE from the patient perspective including signs/symptoms and their impact on domains of HRQoL. The findings from this part may be used to inform the selection, development, or modification of patient-reported outcomes and other endpoints for use in future DLE trials. Subjects will be asked about their experience of signs/symptoms and the impact on HRQoL domains, and any changes in those concepts prior to, during, and following participation in the trial. The interviews will also include questions aiming to understand the subjects' experience with the IMP and with trial procedures. Subjects who withdraw from the trial prior to Week 6 will also be asked about the reason for leaving the trial.

Interviewers will use the semi-structured interview guide to guide the discussion, and the interviews will be audio-recorded and transcribed verbatim for the purpose of accurate analysis. Qualitative analysis of the verbatim transcripts (translated into English) will be performed using thematic analysis. The analysis of the exit interview data will be reported separately as an addendum to the CTR. The interviewers will be trained in potential AE reporting and will report any potential AEs as per trial reporting procedures (Section 13.2).

### **11.6.2 Size of target lesions**

The size of each target lesion will be assessed at the visits indicated in Section 4 and recorded in the eCRF. The longest diameter will be measured in cm (or inches) together with the

diameter perpendicular to this. The area will be calculated in  $\text{cm}^2$  (or  $\text{in}^2$ ). The target lesion area will be estimated by multiplying these 2 dimensions (i.e. longest diameter  $\times$  perpendicular diameter).

### **11.6.3 Photography (optional)**

Subjects will be asked to participate in a photography component involving digital photography for documentation. Participation in this photography component is optional and requires that the subject provides additional informed consent.

Digital colour photographs will be taken of each target lesion according to the schedule of trial procedures (Section 4). At Week 6, photographs should preferably be taken both before and after taking the biopsy (see Section 11.5.3).

For subjects who have provided consent to this part, it will be recorded in the eCRF if the photographs were taken; if not, a comment should be provided.

The trial sites will use their own or sponsor-provided equipment to take the photographs. Instructions for photography standards and procedures will be provided to the sites in a photography manual.

The photographs will have no other subject identifier than the subject ID and will be uploaded electronically to the eCRF under the relevant trial visit.

LEO may at its discretion use the photographs in publications, posters, and similar types of information material or media targeting patients and health care professionals. The photographs may also be part of training material used for training and educational purposes. Steps will be taken to ensure that the identity of the subject is protected to the extent possible.

### **11.7 Estimate of total blood volume collected**

Blood samples will be drawn for haematology, biochemistry, and serology. The total volume of blood to be drawn is less than 100 mL which is much less than the volume of blood drawn during a blood donation (500 mL).

### **11.8 End of trial**

An end of trial form must be completed in the eCRF for all randomised subjects (including subjects who discontinue IMP and subjects who withdraw from trial). The following data will be collected:

- Whether the subject completed the trial.
- Date of trial completion or discontinuation.
- Date and time of last administration of IMPs.
- Last scheduled visit number for which data is recorded.
- If applicable, primary reasons for discontinuation from IMP, withdrawal from trial, and not attending the primary endpoint visit (lack of efficacy, AE, withdrawal by subject, lost to follow-up, pregnancy, death, other).

The end of trial form will be completed when the subject has had their last visit (that is, the early termination visit, the safety follow-up visit, or the primary endpoint visit, whichever comes last).

### **11.9 Storage of biological samples**

Blood and urine safety laboratory samples will not be stored after the safety laboratory analysis is completed. Skin biopsies and non-invasive skin samples (patches) will be retained for as long as the quality of the material permits evaluation but for no longer than 12 months after completion of the CTR, unless specific additional consent has been obtained that allows storage of skin biopsies for future research (see below).

#### *Biobank*

This protocol includes the collection and analysis of different biological samples. If consent is given by the subject, LEO will store the remaining material from the skin biopsies collected in a biobank established by LEO and hosted by BioStorage Technologies GmbH. The residual biological samples will be used for future research performed by LEO. Donation of the samples for future research is voluntary and subjects must give their separate written consent to confirm donation and storage and the terms associated herewith. The samples will be transferred from the relevant laboratory to the biobank. The samples will be labelled with the trial ID, subject ID, and the sample date to protect the privacy of the subjects and to allow continued blinding for future analyses. The samples from this trial will be stored in the biobank for up to 10 years after the end of the trial and will then be destroyed.

## 12 Scientific rationale for trial design and appropriateness of assessments

### 12.1 Scientific rationale for trial design

This is a multi-centre, within-subject, randomised, vehicle-controlled, double-blind trial which will be conducted in accordance with the protocol, ICH-GCP, and applicable regulatory requirements. The primary objective is to demonstrate efficacy of delgocitinib cream 20 mg/g in DLE.

A double-blind design is chosen to prevent any bias from both subject and investigator. The randomisation will minimise selection bias and is considered the most reliable and impartial method of determining differences between treatments. Since this is the first trial with delgocitinib cream in DLE subjects, the cream vehicle will serve as reference to establish the efficacy and safety of delgocitinib.

The within-subject trial design is chosen because it allows direct comparison of delgocitinib cream and vehicle regarding signs of DLE with each subject being their own control which eliminates between-subject variation. This minimises the number of subjects needed which is a great advantage in a rare disease with a scarce patient population. CCI [REDACTED]

The trial population is selected to be homogeneous to reduce the biological variation and thereby reduce the number of subjects needed to evaluate the efficacy of delgocitinib. The eligibility criteria are designed to minimise any risk associated with trial participation (e.g. exclusion of SLE patients with major organ involvement).

Topical application is considered the preferred route of administration for treatments of DLE, since this is a cutaneous disease most often characterised by few lesions affecting small areas of the skin. CCI [REDACTED]

CCI  
[REDACTED]  
[REDACTED]  
[REDACTED]  
[REDACTED]  
[REDACTED]. Based on these considerations, treatment of DLE patients with delgocitinib cream 20 mg/g twice daily (on a BSA of approximately 1%) is expected to be safe and well tolerated.

## 12.2 Appropriateness of assessments

The trial endpoints have been selected to evaluate the efficacy of delgocitinib in reducing the disease activity of DLE. The clinical efficacy of delgocitinib will be assessed using the IGA and specific disease activity scores from the CLASI and RCLASI.

There is no single, standardised grading system for disease severity in DLE. The IGA scale is a static, ordinal, 5-point scale used to rate the subjects' disease from 'clear' to 'severe' (see Section 11.3.1). The scale is defined by distinct and clinically relevant morphological descriptions to minimise inter-rater variation.

The 2 target lesions will be evaluated and scored separately. The IGA scale will allow for an overall qualitative assessment of the disease severity of the target lesions. The scale can be dichotomised to treatment success (score 0 or 1 at Week 6, that is, a  $\geq 2$ -point reduction in IGA score from baseline) and failure, representing a meaningful clinical outcome.

The CLASI and RCLASI have been developed and validated for assessment of disease severity in CLE patients. Both the CLASI and RCLASI score the activity and damage of the disease separately, considering both anatomical region and morphological aspects of skin lesions. In this trial, the skin lesion activity and damage signs scores are applied to the target lesions only. The individual sign scores and sum will give a quantitative assessment of the treatment effect. In addition, full CLASI and RCLASI assessments will be done at screening to describe the overall CLE disease burden in the trial population.

The PaGA is included to capture the subjects' perception of disease severity.

The safety of the IMP will be assessed by vital signs and clinical laboratory measurements and AE monitoring which will include local tolerability.

Skin biopsies (optional) and non-invasive skin samples will be taken for analysis of expression of inflammatory and disease-related genes and biomarkers to explore the molecular components of the disease and drug target engagement (see Section 11.5.1).

Exit interviews have been included as a recognised means of gaining better understanding of the patient experience of disease signs/symptoms and HRQoL impacts, and the IMP and trial procedures (30). Exit interviews are considered particularly valuable in a rare disease such as DLE where there is limited prior literature and knowledge about the patient experience.

## 13 Adverse events

### 13.1 Definition and classification of adverse events

AEs and serious adverse events (SAEs) are defined in Appendix 1.

Classification of AEs in terms of severity, causality, and outcome is defined in Appendix 2.

### 13.2 Collection of adverse event reports

AEs must be collected from time of first trial-related activity after the subject has signed the informed consent form (ICF) until completion of the clinical trial for the individual subject (defined as the safety follow-up visit 2 weeks after last administration of IMP).

AEs must be assessed by medically qualified personnel.

At all visits, the subject will be asked a non-leading question by the investigator about AEs, for example: “How have you felt since I saw you last?” No specific symptoms should be asked for. It is important that the investigator also observes the subject for any changes not reported by the subject and records these changes.

Any potential AEs reported by the subjects during the exit interviews must be collected and documented in the CRO Exit Interview Potential AE Collection Form. The CRO must forward the CRO Exit Interview Potential AE Collection Form to the investigator within 24 hours. The investigator must check if these potential AEs are already recorded in the eCRF. If not, the investigator should contact the subjects for further information to ensure the potential AEs collected by the CRO are recorded in the eCRF as relevant (Section 13.3). If a potential AE qualifies as an SAE, the SAE must be reported as described in Section 13.4.

Refer to Sections 11.4.1 to 11.4.4 for principles for data entry in the eCRF.

### 13.3 Reporting of adverse events

AEs reported by the subject or observed by the investigator must be recorded on the AE form of the eCRF and should be described in the following manner:

The *AE term* must be in precise English medical terminology (that is, not necessarily the exact words used by the subject). Whenever possible, a specific diagnosis should be stated (for example ‘allergic contact dermatitis’).

For cutaneous AEs, the *location* must be part of the AE description and may be described as scalp, forehead, temple, malar, cheek, eyebrow, lower eyelid, upper eyelid, lower lip, upper

lip, chin, external ear, external nose, neck, trunk, arm, or leg. Additionally, the location should be reported as:

- Lesional/perilesional ( $\leq 2$  cm from the border of target lesion(s) treated with IMPs).
- Distant ( $>2$  cm from the target lesion border).

For target lesional/perilesional AEs, the identity of the affected target lesion should be recorded (target lesion 1 or 2).

The *duration* of the AE must be reported by the start date and stop date of the event (it will also be recorded if the event is ongoing). In addition, it will be recorded if the AE started prior to first administration of IMP.

AEs must be classified in terms of severity, causality, and outcome according to the definitions in Appendix 2.

*Action taken with IMP:* any action taken with IMP as a consequence of the AE must be recorded (dose not changed, dose reduced, dose increased, drug interrupted, drug withdrawn, not applicable, unknown).

*Other action taken:* any other action taken as a result of the AE must be recorded (none, concomitant medication, concurrent procedure).

*Withdrawn from trial due to this AE:* it must be recorded whether the AE led to withdrawal from the trial.

## 13.4 Reporting of serious adverse events

The criteria that define an AE as serious (that is, an SAE) are defined in Appendix 1. SAE criteria are also listed on the SAE form.

### 13.4.1 Investigator reporting responsibilities

Any SAE must be reported to LEO on the (paper) SAE form within 24 hours of first knowledge. This report should contain an assessment of available information on seriousness, severity, causal relationship to the IMP or trial procedure, the action taken, the outcome to date, and a narrative description of the course of the event.

The completed SAE form must be faxed or scanned and e-mailed to Global Safety at LEO using the e-mail address or fax number below:

### Global Safety at LEO

E-mail address: [[contact]](mailto:[contact])

[contact]

If relevant, the investigator will enclose other information with the SAE form, such as anonymised reports of diagnostic procedures, hospital records, autopsy reports, etc.

Additionally, Global Safety at LEO may request further information in order to fully assess the SAE. The investigator must forward such information to LEO upon request by fax or e-mail (see contact details above).

The investigator must notify the local IRB(s)/IEC(s) of SAEs, as required by current applicable legislation for the concerned country.

SAEs occurring after the completion of the clinical trial should not be routinely sought or collected. However, such events should be reported to Global Safety at LEO (see contact details above) if the investigator becomes aware of them.

#### **13.4.2 LEO reporting responsibilities**

Global Safety at LEO is responsible for assessing whether or not an SAE is expected. The relevant reference safety information document for the IMP in this clinical trial is:

- The Investigator's Brochure for delgocitinib, edition 2.0 and subsequent updates.

Global Safety at LEO will notify the regulatory authorities and concerned investigators of SAEs according to the current applicable legislation for the concerned countries.

The IRB(s)/IEC(s) will be notified of SAEs according to the current applicable legislation for the concerned countries.

For all non-US countries, the following reporting requirements apply: all SAEs which are assessed as causally related to the IMP(s) by either the investigator or LEO (ICH E2A Guideline), and which are unexpected (Suspected, Unexpected Serious Adverse Reactions [SUSARs]), are subject to expedited reporting to regulatory authorities and/or IEC(s)/IRB(s) according to the current applicable legislation in the concerned countries. Investigators will be notified of the evolving safety profile of the IMP on an ongoing basis.

## 13.5 Other events that require expedited reporting

### 13.5.1 Pregnancy

Any pregnancy occurring after first exposure to IMP and until the subject has completed the trial must be reported to LEO within 24 hours of first knowledge using the (paper) Pregnancy Form (Part I). All pregnancies must be followed up until delivery or termination and final outcome must be reported on the (paper) Pregnancy Form (Part II) within 24 hours of first knowledge.

The completed Pregnancy Forms must be faxed or scanned and e-mailed to Global Safety at LEO. Contact details are given in Section 13.4.1.

Pregnant subjects must immediately discontinue IMP permanently (Sections 10.2.1 and 10.3).

## 13.6 Reporting of other events

### 13.6.1 Adverse events of special interest

The event listed in Panel 11 is considered an AE of special interest (AESI) in this trial based on observations from a trial with delgocitinib cream in subjects with AD. Eczema herpeticum is a known risk for AD patients, but is not expected in DLE patients. If this AESI is observed, the investigator must provide additional details to be recorded in the eCRF. An AESI may be serious (requiring expedited reporting, Section 13.4) or non-serious.

#### Panel 11: Adverse event of special interest

| Adverse event of special interest | Additional information to be provided  |
|-----------------------------------|--|
| Eczema herpeticum.                | Skin findings: 
 
• Lesion type.
 
• Disseminated/localised.
 
• Location.
 
• Present in area with visible eczema/no visible eczema/present in areas with and without eczema.
 
• Monomorphic/polymorphic.
 
 Confirmation of herpes simplex virus. |

### 13.6.2 Overdose

An overdose is defined as a subject using more than double the recommended quantity of IMP specified in this protocol in Section 9.2. An overdose is either accidental or intentional.

The term 'overdose' including a specification of why it occurred (accidental or intentional) must be recorded on the AE form of the eCRF. In addition, AEs originating from overdose must be recorded as separate events. If the AE originating from the overdose qualifies as an SAE, expedited reporting is required (Section 13.4).

### 13.6.3 Medication error

Medication error refers to any unintentional error in the dispensing or administration of an IMP while in the control of the investigator or subject. Broadly, medication errors fall into 4 categories: wrong medication, wrong dose (including strength, form, concentration, amount), wrong route of administration, or wrong subject.

The medication error category must be documented on the AE form in the eCRF. In addition, AEs originating from a medication error must be recorded as separate events. If the AE originating from the medication error qualifies as an SAE, expedited reporting is required (Section 13.4).

### 13.6.4 Misuse

Misuse refers to situations where the IMP is intentionally and inappropriately used not in accordance with the protocol.

The term 'misuse' must be recorded on the AE form in the eCRF. In addition, AEs originating from misuse must be recorded as separate events. If the AE originating from misuse qualifies as an SAE, expedited reporting is required (Section 13.4).

### 13.6.5 Abuse

Abuse relates to the sporadic or persistent, intentional excessive use of an IMP which is accompanied by harmful physical or psychological effects.

The term 'abuse' must be recorded on the AE form in the eCRF. In addition, AEs originating from abuse must be recorded as separate events. If the AE originating from abuse qualifies as an SAE, expedited reporting is required (Section 13.4).

### 13.6.6 Aggravation of condition

Any clinically significant aggravation/exacerbation/worsening of any medical condition(s) (including the trial disease), compared to screening, must be reported as an (S)AE in accordance with Sections 13.3 and 13.4.

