There is a risk that some of the subjects' DLE lesions will get worse during the trial, as 1 target lesion will be treated with vehicle, and topical treatment of other DLE lesions is prohibited during the trial. However, any permanent damage from this is considered very unlikely in this short trial.

The safety of the subjects will be monitored as described in Section 11.4. The risks associated with the invasive procedures in this trial (blood sampling and skin biopsies) are considered minimal. Blood sampling is considered a low risk procedure. Skin biopsies are optional for the subjects. The size of the skin biopsies should not necessitate suturing, but suturing can be performed at the investigator's discretion. A check of skin biopsy wound healing including removal of suture, if applicable, will be performed at the following visit. The risk associated with a skin biopsy, including secondary infection and scarring, is considered low.

In conclusion, the conduct of this trial is considered safe and ethically justified. The associated risk is low and outweighed by the benefit of a potential future treatment for DLE, which is a rare disease with an unmet need for treatment.

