## 10.2 IMP discontinuation rules

### 10.2.1 Reasons for discontinuation of IMP

Subjects will permanently discontinue IMP in the event of:

- An AE that, in the opinion of the investigator or sponsor's medical expert, contraindicates further dosing. This includes unacceptable worsening of DLE symptoms.
- Evidence of pregnancy.
- Clinically important laboratory abnormalities:
  - ALT and/or AST values  $>3\times\text{ULN}$  with total bilirubin  $>2\times\text{ULN}$  (unless elevated bilirubin is related to Gilbert-Meulengracht syndrome).
  - Confirmed ALT and/or AST  $>5\times\text{ULN}$ .

It is not allowed to restart IMP treatment after discontinuation of IMP.

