#### **14.3.9.1 Adverse events**

AEs will be coded during the trial according to Medical Dictionary for Regulatory Activities (MedDRA). AEs will be presented by preferred term and primary system organ class (SOC).

Treatment-emergent AEs will be summarised; however, all AEs recorded during the trial will be included in subject data listings. An event will be considered treatment-emergent if started after the first application of IMP, or if started before the first application of IMP and worsened in severity after first dose of IMP. The tabulations described in the following will only include the treatment-emergent events. In each of the tabulations, AEs are defined by MedDRA preferred terms within primary SOC.

An overall summary of the number of events and the number (percentage) of subjects with any treatment-emergent AEs, deaths, SAEs, premature discontinuations from the trial due to AEs, treatment-related AEs, and severe AEs will be presented.

The number of AEs and number of subjects with each type of AEs will be tabulated. The number of lesion-specific AEs will be tabulated by treatment. The number of lesions with lesion-specific AEs will be cross-tabulated within subject by treatment. The percentage of lesions with AEs will be compared between treatments by McNemar's test.

The severity for each type of AE will be tabulated. Where there are several recordings of severity for a given type of AE, severity will be taken as the most severe recording for that AE. The severity for each type of lesion-specific AE will be tabulated by treatment.

The causal relationship to IMP for each type of AE will be tabulated. Where the investigator has provided several causality assessments for a given type of AE, the information provided in the last AE report will be used for the final causality assessment. The rationale is that by the time the last AE report is completed, the investigator will be in possession of most information and should be able to provide their best causality assessment.

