Related AEs are defined as AEs for which the investigator has not described the causal relationship to IMP as 'not related'. The number of related AEs and the number of subjects with each type of related AE will be tabulated. The number of lesion-specific, related AEs will be cross-tabulated within subject by treatment. The number of lesions with lesion-specific, related AEs will be tabulated by treatment. The percentage of lesions with related AEs will be compared between treatments by McNemar's test.

SAEs will be evaluated separately and a narrative for each will be given.

AESIs and AEs leading to withdrawal from trial or discontinuation of IMP will be listed.

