## **Appendix 1: Definitions of adverse events and serious adverse events**

### **Adverse event definition**

*An AE is defined as any untoward medical occurrence in a patient or clinical investigation subject administered a pharmaceutical product and which does not necessarily have a causal relationship with this treatment. An AE can therefore be any unfavourable and unintended sign (including an abnormal laboratory finding), symptom, or disease temporally associated with the use of a medicinal (investigational) product, whether or not related to the medicinal (investigational) product. (ICH Harmonised Tripartite Guideline for Good Clinical Practice, E6 (R1)).*

This definition includes:

- Accidental injuries.
- Events related to trial procedures.
- Reasons for any unfavourable and unplanned change in medication (drug and/or dose).
- Clinically significant worsening of pre-existing conditions.
- Reasons for admission to hospital or surgical procedures unless these were planned before the subject consented to trial participation.
- AEs commonly observed and AEs anticipated based on the pharmacological effect of the IMP.
- Any laboratory abnormality assessed as clinically significant by the investigator (see Section 11.4.4.2).

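### The pooled lesion-specific AE test counts DLE flares together with local reactions, so an excess of local reactions on delgocitinib can be diluted or masked in that test

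*Combined protocol and SAP*

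**What the plan says.** Four parts of the plan act together.

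- **Reporting.** Section 13.6.6 states that any clinically significant "worsening of any medical condition(s) (including the trial disease), compared to screening, must be reported as an (S)AE". The AE definition in Appendix 1 agrees ("Clinically significant worsening of pre-existing conditions"). So does Section 10.2.1, which, on AEs that rule out further dosing, adds: "This includes unacceptable worsening of DLE symptoms".
- **Attribution to a lesion.** Section 13.3 classes a skin AE up to 2 cm from the border of a target lesion as lesional or perilesional, and adds: "For target lesional/perilesional AEs, the identity of the affected target lesion should be recorded (target lesion 1 or 2"). Since each lesion has one treatment, the event is thereby tied to delgocitinib or vehicle.
- **Analysis.** For lesion-specific AEs, Section 14.3.9.1 says: "The percentage of lesions with AEs will be compared between treatments by McNemar's test". It plans the same test for related AEs. Section 14.3.5 compares counts of related lesion-specific AEs, a secondary endpoint, by a Wilcoxon signed rank test. The rule for relatedness is: "Related AEs are defined as AEs for which the investigator has not described the causal relationship to IMP as 'not related".
- **Expected course.** Section 5.5 names a risk, not a certainty, that "some of the subjects' DLE lesions will get worse during the trial, as 1 target lesion will be treated with vehicle", and adds that topical treatment of other DLE lesions is prohibited.

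None of the planned tests separates worsening of DLE at the target lesion from other lesion-specific AEs.

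**The concern.** The safety objective asks whether delgocitinib harms the treated lesion. In the all-cause comparison, a lesion counts if it has a local reaction, a clinically significant flare, or both. An effective drug prevents flares on its own lesion but not on the vehicle lesion. The contrast then becomes roughly local reactions caused minus flares prevented, and efficacy enters a safety result with the sign that flatters the drug.

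This matters here because Section 5.2 reports no completed trial with the cream and no data in DLE. Section 12.2 also leaves local tolerability to AE monitoring, with no separate tolerability scale in the plan. A small difference in the pooled test could be read as good local tolerability when it is partly a by-product of efficacy.

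**Working it through.** **Inputs.** The plan states no power or expected rate for this comparison, so there is no figure of its own to reproduce. From the documents come a two-sided 5% level (Section 14.3.11), McNemar's test (14.3.9.1), and a safety set of all subjects who received IMP (14.2). The last is about 45 lesion pairs if everyone randomised is treated; 36/0.80 = 45 agrees with Section 14.1. The rates of local reactions and flares are assumptions. The two lesions of a subject are taken as independent.

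**Formulas.** For each lesion, p = 1 − (1 − local)(1 − worsening). Discordant-pair probabilities are b = pD(1 − pV) and c = pV(1 − pD), where D is delgocitinib and V vehicle. With B and C the discordant counts, the test without continuity correction finds an excess on delgocitinib when (B − C)/√(B + C) > 1.96. Detection is the sum of the trinomial probabilities (45; b, c, 1 − b − c) over all such outcomes.

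**All-cause test, local reactions 20% D and 5% V.**

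| Worsening D / V | pD | pV | Difference (points) | Detection |
|---|---|---|---|---|
| none | 0.200 | 0.050 | 15.0 | 57% |
| 2% / 5% | 1 − 0.80×0.98 = 0.216 | 1 − 0.95×0.95 = 0.0975 | 11.9 | 31% |
| 2% / 10% | 0.216 | 1 − 0.95×0.90 = 0.145 | 7.1 | 13% |
| 2% / 15% | 0.216 | 1 − 0.95×0.85 = 0.1925 | 2.4 | 4% |

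In the first row, for example, b = 0.20×0.95 = 0.19 and c = 0.05×0.80 = 0.04.

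**Other assumed rates.** With local reactions of 25% D and 3% V, the difference without flares is 22 points and detection is 89% (83% with the exact test). Worsening of 2% / 5% gives 18.6 points and 65% (56%). Worsening of 3% / 10% gives 14.5 points and 40% (31%). Worsening of 5% / 20% gives 6.4 points and 10% (7%). With local reactions of 15% and 3% and worsening of 5% / 20%, the difference changes sign, to −3.1 points.

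**By counts.** Suppose 9 pairs have a reaction on delgocitinib only and 1 on vehicle only: (9 − 1)²/10 = 6.4, p = 0.011 (exact 0.021). Two further pairs with a flare on vehicle only give (9 − 3)²/12 = 3.0, p = 0.083 (exact 0.146). Five further pairs give (9 − 6)²/15 = 0.6, p = 0.44 (exact 0.61).

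**Related-only McNemar test.** A flare counts here only if it is rated possibly or probably related, so the worsening rate is multiplied by the fraction so rated. Take local reactions of 20% / 5% and worsening of 2% / 10%:

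| Flares rated related | pD | pV | Difference (points) | Detection |
|---|---|---|---|---|
| 0% | 0.200 | 0.050 | 15.0 | 57% |
| 10% | 1 − 0.80×0.998 = 0.2016 | 1 − 0.95×0.99 = 0.0595 | 14.2 | 50% |
| 25% | 1 − 0.80×0.995 = 0.204 | 1 − 0.95×0.975 = 0.0738 | 13.0 | 41% |
| 100% | 0.216 | 0.145 | 7.1 | 13% |

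The signed rank test of the secondary endpoint was not enumerated. It is exposed by the same route.

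**The case against.** A reader might infer that local harm would be hidden from the report. The documents do not support that. Section 14.3.9.1 defines AEs by preferred term within system organ class, and tabulates the severity of each type of lesion-specific AE by treatment. With about 45 subjects, individual reactions would be visible beside DLE worsening. What is missing is an aggregate without flares and a set of terms fixed before unblinding.

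A reader might also infer that the secondary endpoint is affected as much as the all-cause test. It is not. It counts related AEs only, and Appendix 2 lets an investigator call an event not related when the subject's clinical state explains it better. Some leakage remains possible, because Appendix 2 also allows a possible relation when the clinical state is a reasonable alternative explanation.

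The illustrated flare rates may be too high. Only clinically significant worsening is reportable, target lesions enter at IGA 3 or more on a 0 to 4 scale, and daily sunscreen of SPF 50 or higher is required. Section 5.5 also has untreated non-target lesions in view; events more than 2 cm from a target lesion never enter this test. This argues for caution about the larger losses, but it does not remove the mechanism.

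All tests are descriptive (Section 14.3.11), and even without flares detection is only 57% in the first illustration. So no formal safety conclusion hangs on this p-value. A descriptive contrast still needs a clear meaning.

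Finally, all-cause counting is a legitimate safety summary, and irritation by the drug may be recorded as worsening of DLE. Simply excluding those events could remove real harm. That point stands, and it is why both versions are needed.

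**Conclusion.** The point holds in a limited form. Clinically significant DLE worsening at a target lesion enters the all-cause lesion-specific McNemar test. If delgocitinib works, it can offset an excess of local reactions there. The related-AE analyses are affected only to the extent that flares are rated possibly or probably related.

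Under the first set of assumed rates, the all-cause difference shrinks from 15 points to between 11.9 and 2.4, and detection from 57% to between 31% and 4%. In the related-only McNemar test, detection is about 50% or 41% if 10% or 25% of flares are rated related. These sizes rest on assumed rates, 45 pairs and independent lesions, and they show a mechanism rather than a forecast.

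The reporting rule itself is not an error. Harm is masked in one pooled test, not removed from the report. This is a cheap improvement to the interpretation of local tolerability.

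**What to change.** Keep the reporting rule in Section 13.6.6. In Sections 14.3.5 and 14.3.9.1, or in the SAP before unblinding:

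1. At blind review, fix the preferred terms that count as worsening of DLE at the target lesion.
2. Show these events as their own category by treatment.
3. Run the lesion-specific AE comparisons, both all-cause and related, with these events included and with them excluded. Present the two side by side, so that worsening caused by the drug stays visible.

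No new data are needed, because AE term and lesion identity are already recorded (Section 13.3), and Section 14.3.11 already provides for a review on blinded data before the SAP is finalised. The cost is some wording, one or two extra tables, and two versions of each comparison to present and explain.
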